9. RANDOMISATION/BLINDING

9.1. Randomisation

A nurse not involved in the research project performed a computer-generated block randomization, ten patients in each block. The allocation sequence was generated by a software program:

(<http://randomization.com>) and was conducted with a 1:1 ratio between the treatment arms. With 60 patients within each intervention group, twelve blocks of ten patients was needed. 120 sequentially numbered, opaque, sealed envelopes, containing a label describing one of the two interventions, were placed in the operating theatre at operation. The envelope was opened only if the patient fulfilled the inclusion criteria and the baseline assessments. One of the assisting nurses would open the envelopes at the request of the surgeon. The randomization was performed only after the ACL rupture was verified by arthroscopy, and at least 50 % of each menisci was left intact after surgical treatment, and if the hamstring graft sizes were sufficient after harvesting (the minimal desired hamstring graft sizes were 5.0 mm for the PL bundle and 6.0 mm in diameter for the AM bundle).

9.2. Level and method for blinding:

KOOS/IKDC and the activity scales: Initially, the trial participants were not intentionally blinded for the intervention, but the outcome assessor was blinded. The outcome assessor ensured that the PRO from the patients were complete.

The level of blinding was changed during the enrollment, and the study participants number 62 – 120 were consequently blinded for the intervention. Unblinding was performed after the assessments of the two-years follow-up.

Functional tests: The outcome assessor that completed the functional tests, was blinded for the intervention.

Clinical assessment: The clinical assessment was performed by the assisting, orthopaedic surgeon [name]. The surgeon was not blinded, as she was also present during the initial surgery.

Radiographic imaging: The radiologist was not blinded, as the intervention was visible at the radiographic imaging.

Data analysis: The statistical advisor will be blinded when performing the analysis.

10. STATISTICAL METHODS:

10.1. Presentation of observed data

All continuous variables including the five subscores will be summarized with means and standard deviations (SD) within each treatment. Categorical data will be summarized with counts and percentages within each category and treatment arm.

The observed mean values of the primary outcome (KOOS QoL) will be presented in a figure as two curves (one for each treatment) plotted at three different time points (baseline, 1 and two years). Vertical lines at each time point for each treatment will represent the 95% confidence intervals (CIs).

10.2. Primary hypothesis setup

Null hypothesis: Double-bundle ACL reconstruction is equal to single-bundle ACL reconstruction, regarding the change in the KOOS QoL subscale from baseline to the two-years follow-up.

Alternative hypothesis: Double-bundle ACL reconstruction is superior to single-bundle ACL reconstruction, regarding the change in the KOOS QoL subscale from baseline to the two-years follow-up.

10.3. STATISTICAL ANALYSIS

10.3.1. Primary outcome analysis:

The **KOOS QoL subscore** will be analyzed with a linear mixed model with treatment, time point (baseline, 1 year, 2 years), and treatment x time point interaction as fixed effects. A random intercept will be used. Based on the fitted model, we will estimate the mean baseline, 1 year, and 2 years values (with 95% CIs) for each treatment, and the between-treatment difference in changes from baseline to 2 years (with 95% CI and a P-value for the null hypothesis of no difference).

10.3.2. Secondary outcomes analysis:

1. The **KOOS Symptoms** subscore will be analyzed with a linear mixed model with treatment, time point (baseline, 1 year, 2 years), and treatment x time point interaction as fixed effects. A random intercept will be used. Based on the fitted model, we will estimate the mean baseline, 1 year, and 2 years values (with 95% CIs) for each treatment, and the between-treatment difference in changes from baseline to 2 years (with 95% CI and a P-value for the null hypothesis of no difference).
2. The **KOOS Pain** subscore will be analyzed with a linear mixed model with treatment, time point (baseline, 1 year, 2 years), and treatment x time point interaction as fixed effects. A random intercept will be used. Based on the fitted model, we will estimate the mean baseline, 1 year, and 2 years values (with 95% CIs) for each treatment, and the between-treatment difference in changes from baseline to 2 years (with 95% CI and a P-value for the null hypothesis of no difference).
3. The **KOOS Activities of Daily Living** subscore will be analysed with a linear mixed model with treatment, time point (baseline, 1 year, 2 years), and treatment x time point interaction as fixed effects. A random intercept will be used. Based on the fitted model, we will estimate the mean baseline, 1 year, and 2 years values (with 95% CIs) for each treatment, and the between-treatment difference in changes from baseline to 2 years (with 95% CI and a P-value for the null hypothesis of no difference).
4. The **KOOS Sports and Recreation** subscore will be analysed with a linear mixed model with treatment, time point (baseline, 1 year, 2 years), and treatment x time point interaction as fixed effects. A random intercept will be used. Based on the fitted model, we will estimate the mean baseline, 1 year, and 2 years values (with 95% CIs) for each treatment, and the between-treatment difference in changes from baseline to 2 years (with 95% CI and a P-value for the null hypothesis of no difference).
5. The **IKCD 2000 subjective score** will be analysed with a linear mixed model with treatment, time point (baseline, 1 year, 2 years), and treatment x time point interaction as fixed effects. A random intercept will be used. Based on the fitted model, we will estimate the mean baseline, 1 year, and 2 years values (with 95% CIs) for each treatment, and the between-treatment difference in changes from baseline to 2 years (with 95% CI and a P-value for the null hypothesis of no difference).
6. The **Lachman's test** at two years will be analysed with the Wilcoxon-Mann-Whitney test for ordered 2xc tables [REF: Chapter 6 of Fagerland MW, Lydersen S, Laake P (2017) Statistical Analysis of Contingency Tables. Chapman & Hall/CRC, Boca Raton, FL.] A P-value for the null hypothesis that the two treatments have equal distributions across the categories will be presented.
7. The **Pivot shift test** at two years will be analysed with the Wilcoxon-Mann-Whitney test for ordered 2xc tables [REF: Chapter 6 of Fagerland MW, Lydersen S, Laake P (2017) Statistical

Analysis of Contingency Tables. Chapman & Hall/CRC, Boca Raton, FL.] A P-value for the null hypothesis that the two treatments have equal distributions across the categories will be presented.

8. The **KT 1000** measurements, will be analysed with a two-sample T-test, with adjustment for unequal variances (the Welch U test) if the ratio of the largest to the smallest standard deviation is more than 1.5. An estimate of the difference between the mean treatment scores (with a 95% CI), and a P-value for the null hypothesis of no difference, will be presented.
9. The **extension deficit** (range of motion) will be analysed with a two-sample T-test, with adjustment for unequal variances (the Welch U test) if the ratio of the largest to the smallest standard deviation is more than 1.5. An estimate of the difference between the mean treatment scores (with a 95% CI), and a P-value for the null hypothesis of no difference, will be presented.
10. The **flexion deficit** (range of motion) will be analysed with a two-sample T-test, with adjustment for unequal variances (the Welch U test) if the ratio of the largest to the smallest standard deviation is more than 1.5. An estimate of the difference between the mean treatment scores (with a 95% CI), and a P-value for the null hypothesis of no difference, will be presented.
11. The **Tegner activity score** at two years will be analysed with the Wilcoxon-Mann-Whitney test for ordered 2xc tables [REF: Chapter 6 of Fagerland MW, Lydersen S, Laake P (2017) Statistical Analysis of Contingency Tables. Chapman & Hall/CRC, Boca Raton, FL.] A P-value for the null hypothesis that the two treatments have equal distributions across the categories will be presented.
12. The Sports **Activity scale** at two years will be analysed with the Wilcoxon-Mann-Whitney test for ordered 2xc tables [REF: Chapter 6 of Fagerland MW, Lydersen S, Laake P (2017) Statistical Analysis of Contingency Tables. Chapman & Hall/CRC, Boca Raton, FL.] A P-value for the null hypothesis that the two treatments have equal distributions across the categories will be presented.
13. The difference between the treatment probabilities of **Return to sports** will be estimated and a 95% Newcombe hybrid score CI will be reported. The null hypothesis of equal probabilities will be analysed with a Fisher mid-P test [REF: Chapter 4 of Fagerland MW, Lydersen S, Laake P (2017) Statistical Analysis of Contingency Tables. Chapman & Hall/CRC, Boca Raton, FL.]
14. The **One leg hop test** will be analysed with a linear mixed model with treatment, time point (baseline, 1 year, 2 years), and treatment x time point interaction as fixed effects. A random intercept will be used. Based on the fitted model, we will estimate the mean baseline, 1 year, and 2 years values (with 95% CIs) for each treatment, and the between-treatment difference in changes from baseline to 2 years (with 95% CI and a P-value for the null hypothesis of no difference).
15. The **Kellgren-Lawrence classification** at two years will be analysed with the Wilcoxon-Mann-Whitney test for ordered 2xc tables [REF: Chapter 6 of Fagerland MW, Lydersen S, Laake P (2017) Statistical Analysis of Contingency Tables. Chapman & Hall/CRC, Boca Raton, FL.] A P-value for the null hypothesis that the two treatments have equal distributions across the categories will be presented.
16. **Adverse events:** the graft failures and new meniscus injuries will be analysed. The null hypothesis of equal probabilities will be analysed with a Fisher mid-P test [REF: Chapter 4 of Fagerland MW, Lydersen S, Laake P (2017) Statistical Analysis of Contingency Tables.

Chapman & Hall/CRC, Boca Raton, FL.] A P-value for the null hypothesis that the two treatments have equal distributions across the categories will be presented.

17. **Reoperations:** The null hypothesis of equal probabilities will be analysed with a Fisher mid-P test [REF: Chapter 4 of Fagerland MW, Lydersen S, Laake P (2017) Statistical Analysis of Contingency Tables. Chapman & Hall/CRC, Boca Raton, FL.]

Secondary outcome derived from the primary outcome

18. The difference between the probabilities of **treatment failures**, defined as KOOS QoL < 44 points, will be estimated and a 95% Newcombe hybrid score CI will be reported. The null hypothesis of equal probabilities will be analyzed with a Fisher mid-P test [REF: Chapter 4 of Fagerland MW, Lydersen S, Laake P (2017) Statistical Analysis of Contingency Tables. Chapman & Hall/CRC, Boca Raton, FL.]

10.3.3. Subgroup analysis:

A separate analysis of the primary outcome in the blinded versus not blinded patients will be performed. The subgroup would contain patients with randomization number 1-61 versus 62-120. The subgroup analysis will be performed by adding an interaction term between blinded and treatment and an interaction term between blinded and (treatment x time) to the linear mixed model. The P-values for these interaction terms will indicate whether any difference in treatment effects exists between blinded and not blinded patients.

10.3.4. Missing data analysis:

Recording of the reasons for missing data will be done.

The KOOS subscales, the IKDC 2000, and the one leg hop test will be analysed with linear mixed models. These models account for missing data on individual time points, thus obviating the need to impute missing values.

For the categorical and semi-continuous outcomes, we will use a modified ITT analysis set, where only the observed data will be included, if the amount of missing data is less than 5%. For outcomes with more than 5% missing data, a sensitivity analysis will be performed, wherein the missing data will be imputed according to three scenarios:

1. The two year (missing) measurements will be given the values of the one year measurements (or the baseline measurements if the one year measurements are also missing).
2. The two year (missing) measurements will be imputed as the most favourable score for patients who received the double-bundle treatment, and the least favourable score for patients who received the single-bundle treatment.
3. The two year (missing) measurements will be imputed as the least favourable score for patients who received the double-bundle treatment, and the most favourable score for patients who received the single-bundle treatment.

10.4 The timing of analysis:

The final analysis will be performed after the two-years follow-up of all study candidates and after finalization and approval of the statistical analysis plan by all co-authors [name] and the statistical advisor [name]. The statistical analysis plan will be published online on the OSTRC websites before the analysis is performed.

The data will then be prepared and presented to the statistician as blinded data.

The statistical analysis will be performed blinded by the statistical advisor A data collection form will be outlined; the data will have anonymous coding into "treatment 1" and "treatment 2". Analysis of the primary and secondary outcome will be performed blinded and then presented for the other authors.

11. SAFETY ANALYSIS:

11.1. Associated injuries at operation:

Any additional chondral or meniscal injury detected during the index operation will be reported and listed in the summary tables of baseline characters.

11.2. Adverse events:

“An adverse event refers to an untoward occurrence during the trial, which may or may not be causally related to the intervention or other aspects of trial participation” [13]. The study participants were questioned whether they had observed any adverse events related to the treatment during the last year, at the one and two-years follow-up. Each subject were counted once in each category of AE, but each participant could have more than one AE. Any repetition of the same event in one patient was ignored. Additional information about the event was obtained from the patient’s journal if necessary.

11.2.1. Events:

- Bleeding/Hematoma
- Deep venous thrombosis (DVT)
- Injury larger nerves or vessels
- Infection/Septic arthritis
- Arthrofibrosis
- Cyclops
- Donor site morbidity

11.2.2. New injury:

- Meniscal lesion
- Chondral lesion
- Graft re-rupture

11.2.3. New operations:

Because of bleeding/hematoma
Because of injury to larger vessels/nerves
Because of infection
Because of arthrofibrosis
Because of cyclops/extension deficit
Because of donor site morbidity (e.g. removal of fixation device, scar tissue)

Because of Menisci surgery
 Medial menisci resection
 Lateral menisci resection
 Medial menisci suture
 Lateral menisci suture
 Med menisci transplantation
 Lateral menisci transplantation

Because of Cartilage treatment

Because of revision surgery

Others reoperations.

12. PROTOCOL DEVIATIONS:

3.1. Study design:

The hypothesis in the original study protocol was formulated as in a non-inferiority study. Although further evaluations and sample size calculations of the study were designed as in a superiority study design, with the hypothesis questioning if the double-bundle technique was superior to the single-bundle method regarding the KOOS, QoL subscale.

Double-bundle reconstructions are considered more cost demanding, time-consuming and require higher skills of the performing surgeon compared to single-bundle surgery; therefore a superiority study was the preferred study design[22].

2.2. Secondary outcomes:

The Activity scale as one of the PROM's was added after the protocol was made but before inclusion of the first patient.

3.2. Study settings – primary endpoint:

The primary endpoint was changed from five to two-years follow-up, because of a prolonged inclusion period.

3.2. Study settings:

Martina Hansens Hospital was in 2013 implemented as an additional recruiting hospital, because of the prolonged inclusion period and because of the first author worked at both hospitals during this time. The interventions were performed at Oslo University Hospital but were changed to Martina

Hansens Hospital as the operating theatres at Oslo University Hospital were closed down due to rehabilitation, (1st March 2013). The operating surgeon [name] continued to perform the intervention under the same conditions, with the same equipment and fixation devices. (The equipment was transported between the hospitals.)

4. Interventions:

The inclusion criteria for the hamstring tendon graft sizes were changed from 5.5 mm for both bundles to 5.0 mm for the PL bundle and 6.0 mm for the AM bundle, due to the arising difficulties including patients with a sufficient graft size, during the first year of the study.

9.2. Level and method of blinding:

A subgroup of patients, (randomization number 62-120), were blinded for the intervention until they completed the two-years follow-up, to improve the quality of the study. The reason for blinding was to prevent the patients from biasing the results unintentionally, as not blinded studies are known to give larger treatment effects than non-blinded studies.

12.1 Clinical trials, history of changes:

Published at <https://clinicaltrials.gov> 15th of December 2009, (ID: NCT01033188).

5th July 2011:

The name of location has been modified from Ullevaal University Hospital to Oslo University Hospital.

2nd June 2014:

The surgical procedure: Anatomic ACL reconstruction technique was described in detail, and the name of the fixation devices was changed to the devices that was used on the study participants. The minimum hamstring graft size was adjusted from minimum 5.5 mm to 5.0 mm. The sample-size was changed to 112 patients according to the initial sample size calculation.

12th May 2015:

The description of the surgical procedure was further improved to aim the actual anatomic reconstruction that the surgeons performed on all the study participants. The sample size was enlarged to 120 patients because of the block-randomisation, and the anticipated end of study date, changed to 2017.

6th August 2015:

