Menisci surgery including suturing, resection or transplantation.

Reoperations due to cartilage surgery.

Re-arthroscopy due to other reasons.

Revision surgery because of graft rupture, both first and second stage revision surgery.

8. SAMPLE SIZE CALCULATION:

The sample size was calculated as for a superiority study, based on the null hypothesis that quality of life following double-bundle ACL reconstruction is equal to KOOS quality of life following single-bundle ACL reconstruction.

The primary outcome, KOOS QoL subscale, was used for the sample size calculation. A minimal important change (MIC) in QoL of 8 points, has been considered sufficient [23]. With equal allocation in both arms, a standard deviation of 15 points, power of 80%, and assuming a two-sided significance-level of 0.05, the sample size was calculated to be 56 patients in each treatment group.

To allow for 5% drop-outs, the final sample size was set to be 60 patients in each treatment arm, and 120 patients in total.

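### The primary mixed model leaves the baseline mean free in each arm and tests raw change: unbiased, but less precise than a baseline-adjusted analysis of the same data

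*SAP*

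**What the plan says.** Section 10.3.1 specifies a "linear mixed model with treatment, time point (baseline, 1 year, 2 years), and treatment x time point interaction as fixed effects" and a random intercept. The primary test is the between-arm difference in change from baseline to two years. Baseline is one of three outcome visits. It is not a covariate, and nothing makes the two arms share a baseline mean. Section 10.3.2 repeats the model for the other four KOOS subscales, the IKDC 2000 subjective score and the one leg hop test.

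Section 6.1 defines the primary outcome as mean change, and Section 10.2 words the null hypothesis "regarding the change in the KOOS QoL subscale from baseline to the two-years follow-up". Section 8 words its null hypothesis differently: that "quality of life following double-bundle ACL reconstruction is equal to KOOS quality of life following single-bundle ACL reconstruction". Its inputs are "A minimal important change (MIC) in QoL of 8 points, has been considered sufficient", "a standard deviation of 15 points", 80% power, "assuming a two-sided significance-level of 0.05" and equal allocation. They give 56 per arm, raised to 60 for 5% drop-out. No correlation between baseline and follow-up is given.

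Under Section 9.1 the envelope is opened in the operating theatre, once eligibility and the baseline assessments are complete. Section 5.1 requires a completed baseline for the full analysis set.

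**The concern.** With a treatment main effect and a full interaction, the two-year contrast in complete data is the raw difference in change scores: baseline is subtracted with coefficient 1. Because allocation follows the baseline assessment, the treatment difference at baseline is zero by design, and estimating it only adds noise to the primary contrast. With equal SDs, the efficient coefficient on baseline is rho. For a chance baseline difference d, raw change therefore over-corrects by (1 - rho) x d.

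The cost is a wider confidence interval for the primary outcome and for six secondary outcomes, although the data that would narrow it are collected anyway. Section 8 also leaves open whether its SD describes the quantity that Section 10.3.1 tests, so a reader cannot tell what power the planned test has.

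**Working it through.** **Inputs.** From Section 8: difference 8, SD 15, two-sided alpha 0.05, power 80%, 1:1 allocation, 60 per arm with 5% drop-out, so 60 x 0.95 = 57 evaluable per arm. Assumptions: equal SDs at baseline and two years, and rho from 0.2 to 0.7, because the SAP gives no value.

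**Reproducing the plan's figure.** n = 2 x (1.960 + 0.842)² x (15/8)² = 55.2, so 56 per arm, as stated. Power from the noncentral t distribution is 79.9% at 56 and 80.6% at 57 per arm. These hold when 15 is the SD of the quantity tested.

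**Precision.** Let sigma be the SD of the score.
- Planned contrast: SD of change = sigma x sqrt(2(1 - rho)).
- Baseline-adjusted contrast: SD = sigma x sqrt(1 - rho²). Generalised least squares with a common baseline mean, three visits and equal correlations gives the same value.
- Variance ratio, adjusted over planned: (1 - rho²) / (2(1 - rho)) = (1 + rho)/2.

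Sigma cancels, so the ratio does not depend on what the 15 means.

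**Power for 8 points, 57 per arm (noncentral t).** If 15 is the SD of the score, the two SDs are 15 x sqrt(2(1 - rho)) and 15 x sqrt(1 - rho²). If 15 is the SD of change, the adjusted SD is 15 x sqrt((1 + rho)/2).

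| rho | variance ratio | SD of change if 15 = score SD | planned power, 15 = score SD | adjusted power, 15 = score SD | planned power, 15 = change SD | adjusted power, 15 = change SD |
|---|---|---|---|---|---|---|
| 0.2 | 0.60 | 19.0 | 61% | 82% | 81% | 95% |
| 0.3 | 0.65 | 17.7 | 67% | 84% | 81% | 94% |
| 0.4 | 0.70 | 16.4 | 73% | 87% | 81% | 92% |
| 0.5 | 0.75 | 15.0 | 81% | 90% | 81% | 90% |
| 0.6 | 0.80 | 13.4 | 88% | 94% | 81% | 88% |
| 0.7 | 0.85 | 11.6 | 95% | 98% | 81% | 87% |

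**Check on the mixed models themselves.** In 400 simulated trials per setting, with 57 per arm, score SD 15 and equal correlations, the planned model had power 0.66 at rho 0.3 and 0.82 at rho 0.5. The common-baseline model had 0.87 and 0.92.

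**Covariance.** A random intercept imposes one correlation on all pairs of visits. Suppose the correlations are 0.25 (baseline with one year), 0.25 (baseline with two years) and 0.7 (one with two years), an illustrative assumption. The model then works with their mean, (0.25 + 0.25 + 0.7)/3 = 0.40, and takes the variance of change as 2(1 - 0.40) = 1.2 sigma². The true value is 2(1 - 0.25) = 1.5 sigma². The standard error is too small by sqrt(1.2/1.5) = 0.894, and the large-sample type I error is 2 x (1 - Phi(1.96 x 0.894)) = 8%. In simulation under the same correlations, a common-baseline model that kept the random intercept still had a type I error of about 7%. A common baseline mean alone therefore does not secure the nominal level.

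**The case against.** The strongest reply is that the primary analysis contains no error. Sections 6.1, 10.2 and 10.3.1 consistently define, hypothesise and test change, and the estimator is unbiased under randomisation. That stands: this is a point about efficiency, not validity of the contrast.

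A reader might go further and infer that Section 8 powers the trial on the follow-up score, so that the planned test falls short of 80%. The document does not support this. The Section 8 null hypothesis does refer to quality of life after surgery, but the SD is unlabelled, and the same section calls the 8 points a change, as does Section 7.2.1. If 15 is the SD of change, Sections 8 and 10.3.1 agree. Even if it is the SD of the score, a shortfall also needs rho below about 0.5; at 0.6 and 0.7 the planned power exceeds 80%.

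None of this removes the loss of precision, which under equal SDs holds for every rho below 1 and under either reading of the 15.

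**Conclusion.** The planned model gives up precision that the design makes available. With equal SDs at baseline and two years, the adjusted variance is 0.60 to 0.85 of the planned one for rho 0.2 to 0.7. This needs no decision on what the SD of 15 means.

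The effect on power is conditional. Planned power is 61% to 95% over that range if 15 is the SD of the score, and about 81% if it is the SD of change. The SAP settles neither the SD nor rho, so it cannot be said that the trial is underpowered, only that the stated 80% cannot be tied to the planned test as written. Adjusted power is higher than planned power in every case tabulated.

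The random intercept is a related weakness: if follow-up visits correlate more with each other than with baseline, the planned test can exceed its nominal 5%. The change is recommended; without it the primary contrast remains unbiased.

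**What to change.** In Section 10.3.1, drop the treatment main effect at baseline so that both arms share one baseline mean. Keep time, treatment x 1 year and treatment x 2 years, and take the treatment x 2-year coefficient as the primary estimate. Replace the random intercept alone with an unstructured covariance over the three visits. Alternatively, use baseline as a covariate (with a baseline x visit term) and model the one- and two-year scores with an unstructured covariance. Apply the same model in Section 10.3.2 to the other KOOS subscales, the IKDC 2000 and the hop test.

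In Section 8, say what the SD of 15 referred to when the calculation was made and, if known, what correlation was assumed. If this cannot be recovered, say so. It should not be relabelled now to suit the new model.

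The cost is a few sentences of SAP text and no new data. Under randomisation the target difference is unchanged. Section 3.2 shows that recruitment and follow-up have ended, so the sample size can no longer be altered, but the model can. The change should be made and dated before the blinded analysis that Section 10.4 describes.

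### The random-intercept-only primary model gives a correct SE for the baseline-to-2-year contrast only under a covariance assumption that the SAP neither supports nor guards against

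*SAP*

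**What the plan says.** SAP section 10.3.1 analyses KOOS QoL with a "linear mixed model with treatment, time point (baseline, 1 year, 2 years), and treatment x time point interaction as fixed effects". It adds "A random intercept will be used" and takes from the fitted model "the between-treatment difference in changes from baseline to 2 years (with 95% CI and a P-value for the null hypothesis of no difference". The SAP names no residual covariance structure, random slope, robust standard error, check of the assumption or fallback.

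The same specification is repeated in section 10.3.2 for the other four KOOS subscales and IKDC 2000 (items 1 to 5) and for the one leg hop test (item 14). Section 10.3.4 relies on these models in place of imputation.

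Section 8 sets the design inputs: "A minimal important change (MIC) in QoL of 8 points, has been considered sufficient", "a standard deviation of 15 points", 80% power and "assuming a two-sided significance-level of 0.05". It does not say whether the SD is of the score or of the change. No SD by visit and no correlation between visits appears anywhere.

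**The concern.** A random intercept with independent residuals is compound symmetry. It treats baseline, 1 year and 2 years as exchangeable within a patient. Here surgery falls between the first visit and the other two (section 3.2), so exchangeability cannot be taken for granted. Two post-operative scores may well resemble each other more than either resembles the preoperative score.

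The 1-to-2-year change is not part of the primary contrast, yet its variability enters the standard error of that contrast. If it is the least variable of the three changes, it pulls the standard error down. At stake are the width of the primary 95% CI and the 5% level of the one test that decides the trial. With complete data the point estimate is unaffected. With missing visits, a wrong covariance can also shift the estimate, because it governs how the observed visits are weighted.

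**Working it through.** **Step 1. The plan's own figure.** Inputs from section 8: difference 8, SD 15, two-sided 0.05, power 80%, 1:1 allocation. n per arm = 2 × (1.960 + 0.842)² × 15² / 8² = 55.2, rounded up to 56, as stated (the t-test version gives 56.2). Allowing for 5% drop-out, 56 / 0.95 = 58.9, so 59. The stated 60 fits twelve blocks of ten. The sample size is not in error on this point.

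**Step 2. What the model computes.** Number the visits 0 (baseline), 1 and 2, and let Dij be the within-patient change between visits i and j, with Var(Dij) = SDi² + SDj² − 2·rij·SDi·SDj. With complete data and n patients per arm:

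- Random-intercept SE² = (2/n) × [Var(D01) + Var(D02) + Var(D12)] / 3
- Correct SE² = (2/n) × Var(D02)
- True size of the nominal 5% test ≈ 2 × [1 − Φ(1.96 × ratio)], where ratio = random-intercept SE / correct SE

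The two SEs agree when Var(D02) equals the mean of the three variances. With equal SDs this reduces to r02 = (r01 + r12)/2. The ratio then depends only on the correlations, not on the SD or on n.

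**Step 3. One case in full.** Assume SD 15 at every visit, 60 per arm, and r01/r02/r12 = 0.30/0.25/0.70. The change variances are 450 × (1 − r) = 315, 337.5 and 135, with mean 262.5. Random-intercept SE = √(262.5 × 2/60) = 2.96. Correct SE = √(337.5 × 2/60) = 3.35. The ratio is 0.882 and the size 8.4% (8.8% in 40,000 simulated trials).

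**Step 4. The range.** All SDs by visit and all correlations below are assumptions. n = 57 per arm (60 less 5%).

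| SDs (visits 0/1/2) | r01 / r02 / r12 | Random-intercept SE | Correct SE | Ratio | True size |
|---|---|---|---|---|---|
| 15/15/15 | 0.5 / 0.5 / 0.5 | 2.81 | 2.81 | 1.00 | 5.0% |
| 15/15/15 | 0.3 / 0.5 / 0.7 | 2.81 | 2.81 | 1.00 | 5.0% |
| 15/15/15 | 0.4 / 0.4 / 0.5 | 2.99 | 3.08 | 0.97 | 5.7% |
| 15/15/15 | 0.4 / 0.4 / 0.6 | 2.90 | 3.08 | 0.94 | 6.5% |
| 15/15/15 | 0.3 / 0.3 / 0.7 | 2.99 | 3.33 | 0.90 | 7.8% |
| 15/15/15 | 0.5 / 0.25 / 0.5 | 3.04 | 3.44 | 0.88 | 8.4% |
| 15/18/20 | 0.3 / 0.25 / 0.65 | 3.62 | 4.08 | 0.89 | 8.3% |
| 15/15/15 | 0.2 / 0.2 / 0.8 | 3.08 | 3.55 | 0.87 | 9.0% |
| 15/18/15 | 0.3 / 0.3 / 0.5 | 3.39 | 3.33 | 1.02 | 4.6% |
| 15/15/15 | 0.3 / 0.5 / 0.5 | 2.99 | 2.81 | 1.06 | 3.7% |
| 15/20/15 | 0.3 / 0.4 / 0.4 | 3.59 | 3.08 | 1.17 | 2.2% |

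**Step 5. Checks.** Simulations of 20,000 trials gave 7.7% for 0.3/0.3/0.7, 8.7% for 0.5/0.25/0.5, 8.4% for SDs 15/18/20, and 2.2% for SDs 15/20/15. In the same simulations, a test using the variance of the baseline-to-2-year change itself rejected in 4.7% to 5.2% of trials. One fitted REML random-intercept model gave the same SE as the formula (2.8285 by both routes).

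**The case against.** A reader might infer that the primary CI is certainly too narrow and that the type I error exceeds 5%. The SAP does not support that. It gives a single SD and no correlations, and the error can run either way. Nor are equal correlations the only route to a nominal test: 0.3/0.5/0.7 with equal SDs also gives 5.0%. So a 1-to-2-year correlation above the other two does not produce inflation by itself. A mild difference between the correlations matters little (5.7%), and a larger SD at 1 year can cancel or reverse the effect.

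It is also fair to say that the model is pre-specified, that the contrast is clearly defined, that the estimate is sound with complete data, and that the planned drop-out is only 5%, so any harm through missing visits should be small; it has not been quantified here.

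All of this stands against a claim of certain inflation. It does not remove the dependence on an unstated assumption. With equal SDs, the SE is too small whenever baseline correlates no better with year 2 than with year 1 and year 1 correlates better with year 2 than baseline does. That is a natural pattern around surgery. The two clearly conservative rows both need baseline to correlate better with year 2 than with year 1, and one also needs the SD to rise at 1 year and fall back.

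**Conclusion.** The point holds as a conditional one. Under the default reading (the SAP does not itself state that residuals are independent), the primary CI and P-value are correct only if the variance of the baseline-to-2-year change equals the mean of the three pairwise change variances, and nothing in the SAP supports that. Across the scenarios shown, the nominal 5% test has a true size between about 2% and 9%. It is about 6.5% to 9%, with an SE 6% to 13% too small, in the rows where the 1- and 2-year scores are clearly more alike than baseline and 2 years. It is about 2% to 4%, with an SE 6% to 17% too large, in the two clearly conservative rows. Inflation is the likelier direction, but this rests on the timing of surgery and not on any figure in the SAP. The conclusion that the primary test is invalid would go too far. This is a cheap improvement worth making, because it protects the test whichever way the error would run.

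**What to change.** In section 10.3.1, and in section 10.3.2 items 1 to 5 and 14, replace "A random intercept will be used" with text such as: *An unstructured 3x3 within-patient covariance matrix over baseline, 1 year and 2 years will be used, estimated by REML with Kenward-Roger degrees of freedom. If this model does not converge, the random-intercept model will be fitted with robust (sandwich) standard errors.* Settle this before the blinded analysis described in section 10.4.

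The fixed effects, the contrast and the sample size stay as they are. Six covariance parameters are easily estimated from 120 patients with up to 360 observations. The cost is a change of wording and possibly a slightly wider confidence interval.
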